## STATISTICAL ANALYSIS PLAN

- To assess the correlation between anti-*Plasmodium falciparum* antibodies and drug efficacy measures
  - Correlation between specific antibody titres and measures of drug efficacy
- To assess and increase the representability/accuracy of parasite genome sequencing from dry blood spots for the genome sequencing results from leukocyte depleted blood samples
  - Accuracy of SNPs assessment from dry blood spots versus from whole genome sequencing in leukocyte depleted blood samples
  - Candidate markers of resistance identified through genome wide association studies with in vitro parasite drug sensitivity phenotypes
  - Correlation between qPCR-based versus microscopy-based assessments of parasite clearance dynamics
  - Correlation of parasite clearance metrics as assessed by microscopy versus digital microscopy
- To identify differences at the transcriptome level in artemisinin and partner drug sensitive and resistant *P. falciparum* in order to increase the understanding of mechanisms of resistance
  - Comparison of transcriptomic patterns of drug sensitive and resistant parasites before treatment and 6, 12 and 24 hours after start of treatment
- To develop DNA and RNA measurement methods for quantification of male and female gametocytes
  - Levels of RNA transcription coding for male or female specific gametocytes at admission up to day 14, stratified by the presence of gametocytes at enrolment

[figure not shown]
## 2.2. Study design

### Brief Description

This is a multi-centre, partially blinded, randomised, controlled non-inferiority trial of the Triple ACTs artemether lumefantrine + amodiaquine (AL+AQ) and artesunate- mefloquine+piperaquine (ASMQ+PPQ) with the ACTs artemether-lumefantrine + placebo (AL+PBO) and artesunate- mefloquine + placebo (ASMQ+PBO) for the treatment of uncomplicated *Plasmodium falciparum* malaria to

assess and compare their efficacy, safety, tolerability. The study sites are shown in figure 1 below. Patients will be randomized the ratio 1 ACT: 2:matching TACT to one of the following arms: AL+PBO: AL+AQ: AS-PPQ+MQ: AS-PPQ+PBO.

## STATISTICAL ANALYSIS PLAN

**Figure 1 Study sites**

**The study will be done in 8 African countries: Burkina Faso, DR Congo, The Gambia, Guinea, Niger, Nigeria, Tanzania and Rwanda.**

### 2.2.1 Determination of sample size

These studies will have a non-inferiority trial design. Each site will be powered for the efficacy endpoint. For the safety and tolerability endpoint, the sample size will be pooled across the study sites to achieve the desired power of at least 80% to detect rare events.

For sample size calculations, the following assumptions have been used: The expected efficacy of ACTs (AL, ASMQ) in these countries is expected to be approximately 96%. The matching TACT efficacy is assumed to be at least 90% under the null hypothesis of inferiority based on the WHO 90% efficacy threshold. However preliminary TRACII study data suggest that TACTs potentially may have a better efficacy of 1% to 2% higher in favour of TACT (i.e. a conservative 97%-98% efficacy or higher).

A one-sided alpha of 0.025 has been used in sample size calculations as non-inferiority is in one direction. For the efficacy outcome, a sample size of 60 subjects in the ACT plus placebo arms and 120 subjects in the matching TACT would be needed to achieve approximately 80% power to

---

## STATISTICAL ANALYSIS PLAN

detect a non-inferiority margin difference between the group efficacy of -6%. With an additional 20% to cover for loss to follow up, we would therefore need 72 subjects in ACT plus placebo group and 144 subjects in the matching TACT in each of the sites. Since there will be 4 arms, it means we will need 432 subjects per site with 144 subjects in the two ACT arms combined and 288 subjects in the two TACT arms combined.

The sample sizes are in the ratio of 1:2 for ACT vs TACT to allow us to collect more safety and tolerability data for TACTs, which could be beneficial to both policy makers as well as future malaria patients. With these numbers of recruited subjects in Africa, we will have a power above 80% to detect an increase of the incidence of adverse events from 1 in 100 to 3 in 100 for subjects treated with ACT as compared to the matching TACT, respectively.

The sample size calculations were performed using a specialized sample size calculation software, PASS 15.

### 3. Data Analysis

#### 3.1 Trial Profile

The number of patients who will be screened, reasons for non-enrolment, number of patients randomized, number of patients lost to follow up and the number of patients assessed for 42-day endpoint will be summarised in a CONSORT flow diagram, figure 2, below.

## STATISTICAL ANALYSIS PLAN

[figure not shown]

Figure 2 Consort Trial Profile by Arms

---

**STATISTICAL ANALYSIS PLAN**

---

**3.2 Demographics and other baseline characteristics**

The following baseline characteristics will be described by study arm in table 1 (below). Variables such as age, heart rate, respiratory rate will be summarized using median and interquartile range (IQR). Continuous variables such as weight, height, systolic and diastolic blood pressure, QT-intervals, haematocrit and haemoglobin will be summarized using mean and standard deviation or median (IQR) as appropriate. Parasitemia at baseline will be described as geometric mean with range. Categorical variables such as sex, presence of fever, bed net use and gametocytemia at baseline will be summarized using frequencies and percentages.

**Table 1. Baseline characteristics for the participants per study intervention across the sites**

Characteristics	AL+AQ (N=XX)	AL+Placebo (N=XX)	ASMQ+PP Q (N=XX)	ASMQ+Place bo (N=XX)	Total (N=XX)
Female: n (%)	XX(XX.X)	XX(XX.X)	XX(XX.X)	XX(XX.X)	XX(XX.X)
Age (years): median (IQR; range)	XX.X (XX.X- XX.X)	XX.X (XX.X- XX.X)	XX.X (XX.X- XX.X)	XX.X (XX.X- XX.X)	XX.X (XX.X- XX.X)
Age < 12 years: n (%)	XX(XX.X)	XX(XX.X)	XX(XX.X)	XX(XX.X)	XX(XX.X)
Pf asexual parasitaemia at hour 0 (/uL): Geometric mean (range)**	XX.X (XX.X- XX.X)	XX.X (XX.X- XX.X)	XX.X (XX.X- XX.X)	XX.X (XX.X- XX.X)	XX.X (XX.X- XX.X)
Pf asexual parasitaemia at screening (/uL): Geometric mean (range)	XX.X (XX.X- XX.X)	XX.X (XX.X- XX.X)	XX.X (XX.X- XX.X)	XX.X (XX.X- XX.X)	XX.X (XX.X- XX.X)
Gametocyte presence; n(%)	XX(XX.X)	XX(XX.X)	XX(XX.X)	XX(XX.X)	XX(XX.X)
Haematocrit (%): mean (SD)	XX.X (XX.X)	XX.X (XX.X)	XX.X (XX.X)	XX.X (XX.X)	XX.X (XX.X)

## STATISTICAL ANALYSIS PLAN

	XX.X (XX.X- XX.X)	XX.X (XX.X- XX.X)	XX.X (XX.X- XX.X)	XX.X (XX.X- XX.X)	XX.X (XX.X- XX.X)
Weight (kg): median (IQR)	XX.X (XX.X- XX.X)	XX.X (XX.X- XX.X)	XX.X (XX.X- XX.X)	XX.X (XX.X- XX.X)	XX.X (XX.X- XX.X)
Temperature (°C): median (IQR)	XX.X (XX.X- XX.X)	XX.X (XX.X- XX.X)	XX.X (XX.X- XX.X)	XX.X (XX.X- XX.X)	XX.X (XX.X- XX.X)
Fever (>=37.5 °C) n (%)	XX(XX. X)	XX(XX.X)	XX(XX.X)	XX(XX.X)	XX(XX.X)
Respiratory rate (breaths/min): median (IQR)	XX.X (XX.X- XX.X)	XX.X (XX.X- XX.X)	XX.X (XX.X- XX.X)	XX.X (XX.X- XX.X)	XX.X (XX.X- XX.X)
Heart rate (beats/min): median (IQR)	XX.X (XX.X- XX.X)	XX.X (XX.X- XX.X)	XX.X (XX.X- XX.X)	XX.X (XX.X- XX.X)	XX.X (XX.X- XX.X)
Systolic blood pressure (mmHg): median (IQR)	XX.X (XX.X- XX.X)	XX.X (XX.X- XX.X)	XX.X (XX.X- XX.X)	XX.X (XX.X- XX.X)	XX.X (XX.X- XX.X)
Diastolic blood pressure (mmHg): median (IQR)	XX.X (XX.X- XX.X)	XX.X (XX.X- XX.X)	XX.X (XX.X- XX.X)	XX.X (XX.X- XX.X)	XX.X (XX.X- XX.X)
Haemoglobin (g/dL): mean (SD)	XX.X (XX.X)	XX.X (XX.X)	XX.X (XX.X)	XX.X (XX.X)	XX.X (XX.X)
Creatinine (µMol/L): median (IQR)	XX.X (XX.X- XX.X)	XX.X (XX.X- XX.X)	XX.X (XX.X- XX.X)	XX.X (XX.X- XX.X)	XX.X (XX.X- XX.X)
ALT/SGPT (IU/L): median (IQR)	XX.X (XX.X- XX.X)	XX.X (XX.X- XX.X)	XX.X (XX.X- XX.X)	XX.X (XX.X- XX.X)	XX.X (XX.X- XX.X)
AST/SGOT(IU/L): median (IQR)	XX.X (XX.X- XX.X)	XX.X (XX.X- XX.X)	XX.X (XX.X- XX.X)	XX.X (XX.X- XX.X)	XX.X (XX.X- XX.X)

**STATISTICAL ANALYSIS PLAN**

Total Bilirubin (µMol/L): median (IQR)	XX.X (XX.X- XX.X)	XX.X (XX.X- XX.X)	XX.X (XX.X- XX.X)	XX.X (XX.X- XX.X)	XX.X (XX.X- XX.X)
Alkaline Phosphatase (IU/L): median (IQR)	XX.X (XX.X- XX.X)	XX.X (XX.X- XX.X)	XX.X (XX.X- XX.X)	XX.X (XX.X- XX.X)	XX.X (XX.X- XX.X)
QT interval on monitor (milliseconds): median (IQR)	XX.X (XX.X- XX.X)	XX.X (XX.X- XX.X)	XX.X (XX.X- XX.X)	XX.X (XX.X- XX.X)	XX.X (XX.X- XX.X)
Calculated QTc Bazett interval (milliseconds): median (IQR)	XX.X (XX.X- XX.X)	XX.X (XX.X- XX.X)	XX.X (XX.X- XX.X)	XX.X (XX.X- XX.X)	XX.X (XX.X- XX.X)

**3.3 Efficacy of the ACTs and TACTs as defined by the 42-day PCR corrected adequate clinical and parasitological response (ACPR) within each individual site**

Efficacy will be reported as cumulative ACPR cure rates by day 42 estimated by day 42 PCR corrected efficacy and compared between ACT vs TACT. The Kaplan Meier/survival methods will be used to visually show time to . Non-inferiority will be assessed using 95% one side confidence intervals.

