15. STATISTICAL CONSIDERATIONS

15.1. Sample size justification

These studies will have a non-inferiority trial design. Each site will be powered for the efficacy endpoint. For the safety and tolerability endpoint, the sample size will be pooled across the study

sites to achieve the desired power of at least 80% to detect rare events.

For sample size calculations, the following assumptions have been used: The expected efficacy of ACTs (AL, ASMQ) in these countries is expected to be approximately 96%. The matching TACT efficacy is assumed to be at least 90% under the null hypothesis of inferiority based on the WHO 90% efficacy threshold. However preliminary TRACII study data suggest that TACTs potentially may have a better efficacy of 1% to 2% higher in favour of TACT (i.e. a conservative 97%-98% efficacy or higher).

A one-sided alpha of 0.025 has been used in sample size calculations as non-inferiority is in one direction. For the efficacy outcome, a sample size of 60 subjects in the ACT plus placebo arms and 120 subjects in the matching TACT would be needed to achieve approximately 80% power to detect a non-inferiority margin difference between the group efficacy of -6%. With an additional 20% to cover for loss to follow up, we would therefore need 72 subjects in ACT plus placebo group and 144 subjects in the matching TACT in each of the sites. Since there will be 4 arms, it means we will need 432 subjects per site with 144 subjects in the two ACT arms combined and 288 subjects in the two TACT arms combined.

The sample sizes are in the ratio of 1:2 for ACT vs TACT to allow us to collect more safety and tolerability data for TACTs, which could be beneficial to both policy makers as well as future malaria patients [26, 27]. With these numbers of recruited subjects in Africa, we will have a power above 80% to detect an increase of the incidence of adverse events from 1 in 100 to 3 in 100 for subjects treated with ACT as compared to the matching TACT, respectively.

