**Table 2a Comparison of Day 42 PCR corrected Efficacy as proportions of Various ACTs with matching TACTs by sites**

## STATISTICAL ANALYSIS PLAN

Site	PCR corrected ACPR at day 42, n/N, (%)				Risk difference (95% CI, p-value)	
	AL+Placebo (N=XXXX)	AL+AQ (N=XXXX)	ASMQ+Placebo (N=XXXX)	ASMQ + PPQ (N=XXXX)	AL+Placebo vs AL+AQ	ASMQ+Placebo vs ASMQ+PPQ
Burkina Faso	XX/XXX (XX.X)	XX/XXX (XX.X)	XX/XXX (XX.X)	XX/XXX (XX.X)	XX.X (XX.X - XX.X, 0.XXX)	XX.X (XX.X - XX.X, 0.XXX)
DR Congo	XX/XXX (XX.X)	XX/XXX (XX.X)	XX/XXX (XX.X)	XX/XXX (XX.X)	XX.X (XX.X - XX.X, 0.XXX)	XX.X (XX.X - XX.X, 0.XXX)
Gambia	XX/XXX (XX.X)	XX/XXX (XX.X)	XX/XXX (XX.X)	XX/XXX (XX.X)	XX.X (XX.X - XX.X, 0.XXX)	XX.X (XX.X - XX.X, 0.XXX)
Guinea	XX/XXX (XX.X)	XX/XXX (XX.X)	XX/XXX (XX.X)	XX/XXX (XX.X)	XX.X (XX.X - XX.X, 0.XXX)	XX.X (XX.X - XX.X, 0.XXX)
Niger	XX/XXX (XX.X)	XX/XXX (XX.X)	XX/XXX (XX.X)	XX/XXX (XX.X)	XX.X (XX.X - XX.X, 0.XXX)	XX.X (XX.X - XX.X, 0.XXX)
Nigeria	XX/XXX (XX.X)	XX/XXX (XX.X)	XX/XXX (XX.X)	XX/XXX (XX.X)	XX.X (XX.X - XX.X, 0.XXX)	XX.X (XX.X - XX.X, 0.XXX)
Tanzania	XX/XXX (XX.X)	XX/XXX (XX.X)	XX/XXX (XX.X)	XX/XXX (XX.X)	XX.X (XX.X - XX.X, 0.XXX)	XX.X (XX.X - XX.X, 0.XXX)
Rwanda	XX/XXX (XX.X)	XX/XXX (XX.X)	XX/XXX (XX.X)	XX/XXX (XX.X)	XX.X (XX.X - XX.X, 0.XXX)	XX.X (XX.X - XX.X, 0.XXX)
All sites	XX/XXX (XX.X)	XX/XXX (XX.X)	XX/XXX (XX.X)	XX/XXX (XX.X)	XX.X (XX.X - XX.X, 0.XXX)	XX.X (XX.X - XX.X, 0.XXX)

[figure not shown]
[figure not shown]

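### The SAP decides non-inferiority with a one-sided 95% bound (alpha 0.05), but the trial was sized at one-sided alpha 0.025, so the nominal false-claim rate doubles at every site

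*SAP*

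**What the plan says.** SAP section 3.3 covers the primary endpoint, day-42 PCR-corrected ACPR compared between each ACT and its matching TACT within each site. Its whole decision rule is: "Non-inferiority will be assessed using 95% one side confidence intervals". The section does not restate the margin or name an interval method.

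The design alpha appears in protocol section 15.1, and SAP section 2.2.1 repeats it word for word: "A one-sided alpha of 0.025 has been used in sample size calculations as non-inferiority is in one direction". The same text supplies the other design inputs:

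- Control arm: "The expected efficacy of ACTs (AL, ASMQ) in these countries is expected to be approximately 96" per cent.
- Null: "The matching TACT efficacy is assumed to be at least 90% under the null hypothesis of inferiority".
- Alternative: "i.e. a conservative 97%-98% efficacy or higher".
- Margin: the trial is to "detect a non-inferiority margin difference between the group efficacy of -6" per cent.
- Size: "a sample size of 60 subjects in the ACT plus placebo arms and 120 subjects in the matching TACT would be needed", for about 80% power.

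SAP Table 2a, which reports the primary result by site, heads its comparison columns "Risk difference (95% CI, p-value") and leaves space for a lower and an upper limit. It does not say whether the interval is one- or two-sided, or which null hypothesis the p-value tests.

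**The concern.** A one-sided 95% bound uses z = 1.645 and carries a 5% one-sided error rate. A design at one-sided 0.025 uses z = 1.960 and needs a one-sided 97.5% bound. The decision rule and the sample size therefore belong to different tests.

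The mismatch favours the experimental arms. It also recurs at every site, because the primary objective is a within-site comparison.

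If the interval in Table 2a is the usual two-sided one, a site could be declared non-inferior while its displayed interval crosses -6%. Two statisticians following different sections of the same SAP could then report opposite conclusions from the same data.

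**Working it through.** **Inputs** (protocol 15.1 and SAP 2.2.1): ACT efficacy pC = 0.96; TACT efficacy 0.90 at the null and pT = 0.97 to 0.98 at the alternative; margin 0.06; 60 ACT and 120 TACT evaluable; allocation 1:2; power about 80%.

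**1. Which alpha does the stated sample size belong to?** Unpooled normal formula for the control arm:

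n = (z₁₋α + z₀.₈₀)² × [pC(1 − pC) + pT(1 − pT)/2] / (0.06 + pT − pC)²

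With pT = 0.98 the bracket is 0.0384 + 0.0098 = 0.0482 and the denominator is 0.08² = 0.0064.

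- Alpha 0.025: (1.960 + 0.842)² = 7.849, so n = 7.849 × 0.0482 / 0.0064 = 59.1, rounded up to **60** (and 120). This is the plan's own figure.
- Alpha 0.05: (1.645 + 0.842)² = 6.183, so n = 46.6, rounded up to **47** (and 94).

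With pT = 0.97 the formula gives 85 at alpha 0.025 and 67 at alpha 0.05. So 60/120 matches alpha 0.025 at the upper end of the stated efficacy range.

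**2. Power at 60/120 with pT = 0.98.** SE = √(0.0384/60 + 0.0196/120) = 0.0283, and 0.08/0.0283 = 2.82.

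- Alpha 0.025: Φ(2.82 − 1.96) = 80.6%.
- Alpha 0.05: Φ(2.82 − 1.645) = 88.1%.

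**3. Shift in the bound.** (1.960 − 1.645) × SE = 0.315 × 2.83 points, about 0.9 percentage points.

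**4. Exact operating characteristics.** Sum Bin(x; 120, pT) × Bin(y; 60, pC) over all outcomes (x, y) for which non-inferiority would be declared. The SAP names no interval method, so two are shown.

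| True TACT / ACT | Method | Claims at alpha 0.025 | Claims at alpha 0.05 |
|---|---|---|---|
| 90% / 96% (null) | Score (Farrington-Manning) | 2.8% | 5.1% |
| 90% / 96% (null) | Wald | 2.1% | 4.5% |
| 96% / 96% | Score | 52.8% | 66.0% |
| 97% / 96% | Score | 71.5% | 81.7% |
| 98% / 96% | Score | 88.2% | 93.1% |

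The nominal false-claim rate doubles exactly (0.05/0.025). The actual rate rises about 1.8-fold with the score test (5.1/2.8) and 2.1-fold with Wald (4.5/2.1). When the arms are equal, or the TACT is one point better, about 10 to 13 in 100 site comparisons change verdict with the choice of rule.

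**5. A result that flips.** ACT 58/60 (96.67%) and TACT 115/120 (95.83%) differ by −0.83 points. SE = √(0.9583 × 0.0417/120 + 0.9667 × 0.0333/60) = 0.0295.

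- SAP 3.3 as written: −0.0083 − 1.645 × 0.0295 = −5.7%, non-inferior.
- Design alpha: −0.0083 − 1.960 × 0.0295 = −6.6%, not shown.

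The score statistic is 1.75, between 1.645 and 1.960, so the verdict flips under that method too. So does TACT 116/120 against ACT 59/60 with Wald limits: −5.5% against −6.2%.

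**The case against.** The strongest reply is that the sentence in SAP 3.3 is loosely drafted and means one side, the lower limit, of an ordinary 95% interval. That would be exactly alpha 0.025. The reading fits section 2.2.1 and the two-limit intervals in Table 2a, and no table has a place for a single one-sided bound. The preceding sentence in 3.3 is visibly unfinished, which supports hasty drafting.

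That reading is possible, but the text does not state it, and nothing says the tabulated interval replaces the rule. The literal meaning is the more permissive one. A primary decision rule should have one reading, fixed before the data are seen.

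Some narrower points stand:

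- Doubling is exact only for the nominal rate.
- A site could, rather than will, be declared non-inferior with an interval crossing -6%; the estimate has to fall in a band about 0.9 points wide.
- The power figures depend on method. The loss from restoring 0.025 is about 7 points by formula (88.1% to 80.6%) and about 5 points by exact score enumeration (93.1% to 88.2%).
- With 15 comparisons (8 AL pairs, 7 ASMQ pairs), the chance of at least one false claim is 1 − 0.95¹⁵ = 54% against 1 − 0.975¹⁵ = 32%. This assumes independence and every pair sitting at the margin, and protocol section 7 lets sites run one pair only. It illustrates a separate multiplicity question, and the conclusion does not rest on it.
- The unspecified null for the Table 2a p-value is a related but minor omission.

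**Conclusion.** The concern holds. As written, the SAP's primary decision rule contradicts its own sample size section and the protocol. It sets the nominal false non-inferiority rate at 5% instead of 2.5% in each site comparison. The exact rates are 5.1% against 2.8% (score) or 4.5% against 2.1% (Wald), assuming 60 and 120 evaluable subjects and true efficacies of 96% and 90%. The sample size confirms that 0.025 was the design intent. The conflict concerns the primary endpoint and can change site-level conclusions in favour of the TACTs, so it must be resolved before the primary comparison is made.

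**What to change.** Replace the sentence in SAP 3.3 with:

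> Non-inferiority is concluded if the lower limit of the two-sided 95% confidence interval (equivalently, the one-sided 97.5% bound) for the difference TACT minus ACT in day-42 PCR-corrected ACPR lies above −6 percentage points.

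Name the interval method in the same place. Label the interval in Table 2a and Figure 3 as that two-sided 95% interval, with the direction TACT minus ACT. If a p-value is kept in Table 2a, define it as the test of a difference of −6 points or worse.

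The cost is one sentence and some labels. Sample size, data collection and conduct do not change. The plan gives up power it was never designed to have: by formula at TACT 98%, power returns from 88.1% to the planned 80.6%. If the sponsor does intend one-sided 0.05, the SAP should say so, justify the departure from protocol 15.1, and bring section 2.2.1 into line.

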***Handling of missing data***

In the ITT analysis in which efficacy will be reported as proportions of outcomes using Complete case Analysis.

In the PP analysis in which efficacy will be reported as proportions of outcomes, patients in which study drugs are discontinued and/or endpoints are not available due to other reasons (such as withdrawal from the study, loss to follow up, *P falciparum* (Pf) or *P vivax* (Pv) reinfections and inconclusive PCR correction) will be excluded from the analysis.

[figure not shown]
In the Kaplan-Meier/survival analysis subjects in which study drugs are discontinued and/or endpoints are not available due to other reasons (such as withdrawal from the study, loss to follow up, Pf or Pv reinfections and inconclusive PCR correction) will be censored or treated as competing risks, as appropriate, from the moment of occurrence of one of these events.

Similar analyses as secondary endpoints will be performed for day 63 PCR corrected efficacy and day 42 and day 63 the PCR uncorrected data as well. Where applicable, we will also report the cumulative reinfection rate. The treatment efficacy, 95% confidence intervals and p-values for the comparison of ACTs with matching TACTs will be presented as outlined in tables 2, 3, 4 and 5 below.

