10.4. Rescue treatment

The indication for rescue treatment is:

- The development of any danger signs or signs of severe malaria at any point.

Rescue treatment will consist of parenteral artesunate (per WHO Treatment Guidelines, 3rd edition, 2015) as below:

- For subjects <20 kg bodyweight, 3 mg/kg IV/IM STAT, followed by 3 mg/kg IV/IM at 12 hours and 24 hours and then daily until able to take oral medication
- For subjects ≥ 20 kg bodyweight, 2.4 mg/kg IV/IM STAT, followed by 2.4 mg/kg IV/IM at 12 hours and 24 hours and then daily until able to take oral medication.

If needed, the rescue treatment will be adjusted to local guidelines.

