11. DISCONTINUATION/ WITHDRAWAL OF PARTICIPANTS FROM THE STUDY

Each participant has the right to discontinue the study drug or withdraw from the study at any time. Data accrued up until the time of discontinuation/withdrawal will be used in the analysis, unless the subject wishes to withdraw even the data which has already been collected in which case those data will be excluded as well.

In general, the investigator must make every effort to perform the study procedure until day 63.

In principle the following situations are NOT reasons to discontinue the patient from the study:

- Significant non-compliance with treatment regimen or study requirements
- An adverse event which requires discontinuation of the study medication or results in inability to continue to comply with study procedures

- Disease progression which requires discontinuation of the study medication or results in inability to continue to comply with study procedures
- Development of severe malaria
- Recurrent parasitaemia
- Loss to follow up (every attempt should be made to re-contact the participant)
- Discontinuation of the study drug

However, the investigator may discontinue participation in the study of a participant if he or she considers it necessary.

In addition, the participants always have the right to withdraw consent in writing or verbally.

The reason for withdrawal or discontinuation, if available, will be recorded in the CRF. If the study drug or participation in the study is discontinued due to an adverse event, the investigator will arrange for follow-up visits at least until the adverse event has resolved or stabilised.

Any pregnancy must be reported to the Principal Investigator within one working day of awareness. The PI must take all reasonable efforts to discover the outcome of the pregnancy and fill out the pregnancy form. If there is a congenital abnormality or a still born baby, this needs to be reported as a serious adverse event.

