## STATISTICAL ANALYSIS PLAN

### 1. Analysis Considerations

#### 1.1 General Analysis Approach

The main analysis strategy for the primary outcome will be the intention-to-treat (ITT) principle. In this analysis, patients will be analysed according to the arm of randomisation irrespective of the treatment that was actually given. Complete Case Analysis will be used in the ITT analysis population (Groenwold et al 2012; Mukaka et al 2016; Sullivan et al 2018). Furthermore, the estimates of efficacy using survival analysis will be done. This approach will help in handling missing data as all patients will be included in the analysis and censored at their last follow-up time. These ITT analyses will be followed by the per protocol (PP) analysis. In this analysis only those that adhered to the protocol with respect to the primary outcome will be included for analysis of the primary outcome.

Key secondary endpoints such as parasite clearance parameters (e.g. half-lives), safety and tolerability data will be analysed similar to the ITT approach for the main primary outcome. In this analysis, patients will be analysed according to the arm of randomisation irrespective of the treatment that was actually given and all patients will be included in the analyses irrespective of their follow-up status as long as they have the data. Withdrawals and losses to follow up will not affect the analyses of this data as long as the relevant data needed for these analyses is available prior to withdrawal or loss to follow up.

Data analysis will mainly be performed using Stata 17 or higher, StataCorp, [name] or in R software.

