#### 2.1.2. Primary endpoint

42-day efficacy defined as PCR-corrected adequate clinical and parasitological response (ACPR).

*(NB, WHO definition of ACPR: absence of parasitaemia at day 42 irrespective of axillary temperature and without previously meeting any of the WHO criteria for early or late treatment failure, or late parasitological failure.)*

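### SAP 3.3 removes patients whose study drug was stopped from the per-protocol proportions, and censors them in the survival analysis, with no exception for those who had already failed treatment

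*SAP*

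**What the plan says.** SAP 1.1 makes ITT with complete cases the main strategy for the primary outcome. It adds a survival analysis and then a PP analysis, defined thus: "In this analysis only those that adhered to the protocol with respect to the primary outcome will be included".

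Under the missing-data heading of SAP 3.3, the PP proportions leave out "patients in which study drugs are discontinued and/or endpoints are not available due to other reasons". The examples given are withdrawal, loss to follow-up, reinfection and inconclusive PCR. The survival rule opens in the same way, "In the Kaplan-Meier/survival analysis subjects in which study drugs are discontinued and/or endpoints are not available due to other reasons", and those subjects are censored or treated as competing risks from that moment. The ITT proportion rule has no discontinuation clause. The section applies similar analyses to day 63 and to the PCR-uncorrected endpoints.

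SAP 2.1.2 grants ACPR only to a patient free of parasites at day 42 "without previously meeting any of the WHO criteria for early or late treatment failure, or late parasitological failure".

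Protocol 10.4 gives the indication for rescue as "The development of any danger signs or signs of severe malaria at any point", and states: "Rescue treatment will consist of parenteral artesunate". Protocol section 11 lists situations that are in principle not reasons to take the patient out of the study. One of them is "Disease progression which requires discontinuation of the study medication or results in inability to continue to comply with study procedures"; development of severe malaria is another.

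**The concern.** A patient who meets a failure criterion while still on study drug, and whose drug is then stopped, has a known primary outcome: failure. The SAP handles that patient under missing data. As written, the patient leaves both numerator and denominator of the PP proportion and is not an event in the survival analysis.

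In a non-inferiority trial, PP is read beside ITT because it is expected to be less likely to make the arms look alike by default. A PP rule that discards real failures works against that purpose. At the planned size few failures are expected in either arm (60 x 4% = 2.4 on ACT; 120 x 2% = 2.4 on TACT), so the handling of single patients matters.

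**Working it through.** **Inputs.** From SAP 2.2.1: ACT efficacy 96%; TACT 97-98% expected and 90% under the null; margin -6 points; one-sided alpha 0.025; 60 ACT and 120 TACT evaluable per matching pair and site. From protocol Appendix 2: last dose at 48 h (ASMQ arms) or 60 h (AL arms). The share of failures that occur during dosing with study drug stopped is in neither document; it is called f below and is an assumption.

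**Step 1. Reproduce the plan's figure.** With unpooled variance and 1:2 allocation,

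n(ACT) = (1.960 + 0.842)² x [0.96 x 0.04 + 0.98 x 0.02 / 2] / (0.98 - 0.96 + 0.06)² = 59.1, rounded up to 60, with 120 on TACT (power 80.6%).

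The stated 60/120 is therefore reproduced, at TACT efficacy 98%. The same sizes and margin are used below.

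**Step 2. Average effect on the margin.** Take true rates of 96% and 90% and drop a share f of failures in both arms. The expected PP rates are 0.96 / (1 - 0.04f) and 0.90 / (1 - 0.10f). The last column is the simulated chance that the PP lower limit (z = 1.96, unpooled) lies above -6 points, from 200,000 runs.

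| f | PP rate ACT | PP rate TACT | Difference | Non-inferiority declared |
|---|---|---|---|---|
| 0 | 96.00% | 90.00% | -6.00 | 2.1% |
| 10% | 96.39% | 90.91% | -5.48 | 3.3% |
| 20% | 96.77% | 91.84% | -4.94 | 5.0% |
| 30% | 97.17% | 92.78% | -4.38 | 7.7% |
| 50% | 97.96% | 94.74% | -3.22 | 20.3% |

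Dropping the same share from both arms shrinks the difference, because the arm with more failures loses more of them.

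**Step 3. One site, to see how far single patients matter.** Lower limit = d - z x sqrt[pT(1 - pT)/nT + pC(1 - pC)/nC]. All counts are invented. ACT has 2 failures in 60. TACT has 5 in 120, or 7 in 120 in the last pair of rows.

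| Handling | TACT | ACT | d | Lower limit, z = 1.96 | Lower limit, z = 1.645 |
|---|---|---|---|---|---|
| All counted | 115/120 | 58/60 | -0.83 | -6.61 | -5.68 |
| Two TACT failures dropped | 115/118 | 58/60 | +0.79 | -4.57 | -3.71 |
| One dropped per arm | 115/119 | 58/59 | -1.67 | -6.29 | -5.54 |
| Seven TACT failures, all counted | 113/120 | 58/60 | -2.50 | -8.68 | -7.69 |
| Four of the seven dropped | 113/116 | 58/60 | +0.75 | -4.64 | -3.77 |

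Both values of z are shown because the SAP is not consistent: section 2.2.1 uses one-sided 0.025, while section 3.3 calls for one-sided 95% intervals. Dropping two TACT failures moves the result across -6 at z = 1.96 but not at z = 1.645. Dropping four moves it across at both. Dropping one per arm moves the difference against TACT and changes no conclusion at either level.

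**The case against.** Four points carry weight.

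- **The main analysis is sound here.** The ITT proportion has no discontinuation exclusion and the patient stays in follow-up, so the failure can be counted there. A reader might infer that the rule hides any excess of early failures on TACT, or undermines the primary result. The documents do not support that.
- **The chain from rescue to exclusion is not complete in the text.** Protocol 10.4 does not say that study drug stops when rescue starts. SAP 2.1.2 refers to WHO criteria without listing them, so it cannot be shown that every child with a danger sign is a treatment failure. A reader might infer that every rescued child is a failure who disappears from PP; the documents do not establish this. They show only that stopping drug for disease progression is foreseen, and that a patient who has met a failure criterion is not ACPR.
- **The window is short.** After the last dose there is no study drug left to stop, so recurrences and persistent parasitaemia treated from day 7 are untouched.
- **Another reading exists.** The rule stands under missing data, and its closing words about other reasons could be meant to exclude treatment failure. Protocol-directed rescue is also not obviously non-adherence under SAP 1.1. But the sentence joins discontinuation to unavailable endpoints by *and/or*, and the limiting words follow only the second limb. If the narrower meaning was intended, it needs to be written down.

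The first three points limit scope and frequency. None of them supplies the missing exception.

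**Conclusion.** The point holds with a limited scope. As written, SAP 3.3 removes from PP, and does not count as an event in the survival analysis, a patient who met a failure criterion at or before study-drug discontinuation. It concerns failures up to 48 or 60 hours and leaves the main ITT proportion intact. The survival estimates are affected, although SAP 1.1 places them among the ITT analyses.

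The size cannot be fixed from the documents. On the margin, with equal shares dropped in both arms, the PP false-positive risk goes from about 2.1% to 3.3% (10% dropped), 5.0% (20%) or 7.7% (30%). These shares are assumptions. A changed conclusion at a single site depends on which arm loses failures and on the interval level used, so the single-site example shows sensitivity and should not be read as the expected effect.

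**What to change.** Add one sentence to SAP 3.3, for example: *A patient who meets a protocol or WHO treatment-failure criterion at or before study-drug discontinuation is counted as a failure on that date in the PP and survival analyses, as in ITT; exclusion (PP), or censoring or competing-risk handling (survival), because of discontinuation applies only to patients who had not met a failure criterion.*

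Discontinuations without failure, such as the QT/QTc stops in protocol 9.6, remain under the present rule. The cost is one sentence and a matching line in the analysis program. No clinical rule, visit, sample size or data item changes.
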